6.5.5.1. Main Analysis

The key secondary endpoint will be analyzed in the ITT set with participants grouped according to the treatment assigned at randomization.

A MMRM model will be used to analyze the key secondary endpoint. The model will include fixed categorical effects for treatment group, visit, disease type (C3G vs IC-MPGN), stratification factors, and the visit-by-treatment group interactions, as well as the continuous, fixed covariate of baseline eGFR values. Further details on the presentation of the results are described in Section 6.1. Strategies for addressing ICEs are the same as the ones described in Section 6.4.1. The randomization seed to be used is CCI.

The observed values for eGFR will be summarized by treatment group and visit. Summaries will present the descriptive statistics for baseline, absolute values, change and percentage change from baseline data by visit.

The mean change from baseline in eGFR (±SE) will be plotted over time by treatment group.

All eGFR data will be listed for the ITT set.

6.5.5.2. Sensitivity Analyses

The two sensitivity analyses method described in Section 6.4.2 will be repeated for the key secondary endpoint. For tipping point analysis, the range of the shift parameters will be from -1.3 to -6.5 by increments of -1.3.

6.5.5.3. Supplemental Analyses

6.5.5.3.1. Per Protocol Set

The main analysis described in Section 6.5.5.1 will be repeated using the PP set to investigate the impact of changing the population in the estimand. Missing data (regardless of the reason being the ICEs or not) will be handled implicitly within the MMRM analysis under the assumption of missing at random (MAR).

6.5.5.3.2. Slope Analysis

The mean rate of change (ie, slope) in observed eGFR values will be compared between treatment groups using the linear mixed effects model for slope analysis of continuous outcomes described above in Section 6.1. The mean rate of change (slope), standard errors, and confidence interval will be estimated for the baseline to week 26 period for each treatment group. In addition, the estimated difference in slopes between the treatment groups along with the 95% CIs and p-value will be reported.

6.5.5.4. Subgroup Analyses

Subgroup analyses will be performed for this key secondary endpoint to evaluate the consistency of the results across the subgroups specified in Section 6.4.4.

6.6. Analyses of Additional Secondary Efficacy Endpoints

The following subsections describe the analyses of the additional secondary efficacy endpoints of the study. All analyses of the additional secondary efficacy endpoints will be done on the ITT set.

6.6.1. The Proportion of Participants Achieving Proteinuria <1 g/day

The additional secondary efficacy endpoint of the proportion of participants achieving proteinuria <1 g/day (assessed by 24-hour urine protein) at week 24 will be examined with the following null ($H_{7,0}$) and alternative ($H_{7,1}$) hypotheses:

- H_{7,0}: There is no difference in proportion of participants who achieve proteinuria <1 g/day at week 24 between the pegcetacoplan and placebo treatment groups.
- H_{7,1}: There is a difference in proportion of participants who achieve proteinuria <1 g/day at week 24 between the pegcetacoplan and placebo treatment groups.

The additional secondary endpoint will be analyzed in the ITT set with participants grouped according to the treatment assigned at randomization.

A logistic model will be used to analyze the additional secondary endpoint. The model will include treatment group as the independent variable and adjusted for baseline proteinuria values, disease type (C3G vs IC-MPGN), and stratification factors. Further details on the presentation of the results are described in Section 6.1. Strategies for addressing ICEs are the same as the ones described in Section 6.5.1.1.

The numbers and proportion of participants achieving proteinuria <1 g/day at week 24 will be tabulated by treatment group.

All 24-hour urine protein data will be listed for the ITT set.

6.6.2. The Proportion of Participants With Normalization of Serum Albumin Levels

For participants with serum albumin levels below LLN at baseline, the additional secondary efficacy endpoint of the proportion of participants with normalization of serum albumin levels at week 26 will be examined with the following null (H_{8,0}) and alternative (H_{8,1}) hypotheses:

- H_{8,0}: There is no difference in proportion of participants who achieve normalization of serum albumin levels at week 26 between the pegcetacoplan and placebo treatment groups.
- H_{8,1}: There is a difference in proportion of participants who achieve normalization of serum albumin levels at week 26 between the pegcetacoplan and placebo treatment groups.

The serum albumin levels status at week 26 will be calculated using the following steps:

- 1. Baseline serum albumin value will be calculated as the average of up to 2 serum albumin measurements preceding and including day 1. Participants will be included in the denominator of this calculation only if the baseline albumin value is below the LLN.
- 2. Week 26 serum albumin values will be calculated as the average of up to 2 serum albumin measurements preceding and including week 26, no earlier than week 20 measurement.

3. Each participant will be categorized as either a success or a failure according to whether the week 26 serum albumin values as calculated in Step 2. Values greater than or equal to the LLN will be categorized as a success; values less than the LLN will be categorized as a failure.

The additional secondary endpoint will be analyzed in the ITT set with participants grouped according to the treatment assigned at randomization.

A logistic model will be used to analyze the additional secondary endpoint. The model will include treatment group as the independent variable and adjusted for baseline albumin value, disease type (C3G vs IC-MPGN), and stratification factors. Further details on the presentation of the results are described in Section 6.1. Strategies for addressing ICEs are the same as the ones described in Section 6.5.1.1.

For participants with serum albumin levels below the LLN at baseline, the numbers and proportion of participants with normalization of serum albumin levels at week 26 will be tabulated by treatment group. The observed values for serum albumin will be summarized by treatment group and visit.

All serum albumin data will be listed for the ITT set.

6.6.3. The Proportion of Participants With Serum C3 Levels Above the LLN

For participants with serum C3 levels below the LLN at baseline, the additional secondary efficacy endpoint of the proportion of participants with serum C3 levels above the LLN at week 26 will be examined with the following null (H_{9,0}) and alternative (H_{9,1}) hypotheses:

- H_{9,0}: There is no difference in proportion of participants with serum C3 levels above the LLN at week 26 between the pegcetacoplan and placebo treatment groups.
- H_{9,1}: There is a difference in proportion of participants with serum C3 levels above the LLN at week 26 between the pegcetacoplan and placebo treatment groups.

The serum C3 levels status at week 26 will be calculated using the following steps:

- 1. Baseline serum C3 value will be calculated as the average of up to 2 serum C3 measurements preceding and including day 1. Participants will only be included in the denominator of this calculation if the baseline C3 value is below the LLN.
- 2. Week 26 serum C3 value will be calculated as the average of up to 2 serum C3 measurements preceding and including week 26, no earlier than week 20 measurement.
- 3. Each participant will be categorized as either a success or a failure based on whether the week 26 serum C3 value as calculated in Step 2. Values greater than or equal to the LLN will be categorized as a success; values less than the LLN will be categorized as a failure.

The additional secondary endpoint will be analyzed in the ITT set with participants grouped according to the treatment assigned at randomization.

A logistic model will be used to analyze the additional secondary endpoint. The model will include treatment group as the independent variable and adjusted for baseline serum C3 level, disease type (C3G vs IC-MPGN), and stratification factors.

Further details on the presentation of the results are described in Section 6.1. Strategies for addressing ICEs are the same as the ones described in Section 6.5.1.1.

For participants with low serum C3 levels at baseline, the numbers and proportion of participants with serum C3 levels above the LLN at week 26 will be tabulated by treatment group. The observed values for serum C3 will be summarized by treatment group and visit.

All serum C3 level data will be listed for the ITT set.

6.6.4. Change From Baseline in FACIT-Fatigue Scale Score

The additional secondary efficacy endpoint is the FACIT-Fatigue score at week 26. It will be examined with the following null $(H_{10,0})$ and alternative $(H_{10,1})$ hypotheses:

H_{10,0}: There is no difference in mean change from baseline to week 26 in FACIT-Fatigue score between the pegcetacoplan and placebo treatment groups.

H_{10,1}: There is a difference in mean change from baseline to week 26 in FACIT-Fatigue score between the pegcetacoplan and placebo treatment groups.

The additional secondary endpoint will be analyzed in the ITT set with participants grouped according to the treatment assigned at randomization.

The FACIT-Fatigue score is constructed as the total score of the 13 questions. Each question has 5 possible responses as "Not at all" (0), "A little bit" (1), "Somewhat" (2), "Quite a bit" (3) and "Very much" (4). Before calculating the total score, some responses are reversed to ensure that the higher score corresponds to a higher quality of life.

An ANCOVA model will be used to analyze the additional secondary endpoint. The model will include treatment as a fixed effect, adjusted for baseline FACIT-Fatigue score, disease type (C3G vs IC-MPGN), the stratification factor of transplant status, and age group (adults vs. adolescents). Further details on the presentation of the results are described in Section 6.1. Strategies for addressing ICEs are the same as the ones described in Section 6.4.1. The randomization seed to be used is

The observed values for FACIT-Fatigue score will be summarized by treatment group and visit. Summaries will present the descriptive statistics for baseline, absolute values, change and percentage change from baseline data by visit. Note that the FACIT-Fatigue questionnaires have two versions, one for adults and one for adolescents. The summaries will be pooled together regardless of the different versions. Additional analysis on modeling the adults and adolescents separately will also be performed.

All FACIT-Fatigue score data will be listed for the ITT set.

6.6.5. Change From Baseline in KDQOL Score

The additional secondary efficacy endpoint is the KDQOL score at week 26. It will be examined with the following null $(H_{11,0})$ and alternative $(H_{11,1})$ hypotheses:

- H_{11,0}: There is no difference in mean change from baseline to week 26 in KDQOL score between the pegcetacoplan and placebo treatment groups.
- H_{11,1}: There is a difference in mean change from baseline to week 26 in KDQOL score between the pegcetacoplan and placebo treatment groups.

The additional secondary endpoint will be analyzed in the ITT set with participants grouped according to the treatment assigned at randomization.

The KDQOL score is constructed as the KDQOL-36 Summary Score (KSS) by averaging the 24 items from Burden of Kidney Disease, Symptoms and Problems of Kidney Disease, and Effects of Kidney Disease on 0-100 scale (Peipert et al. 2019).

An ANCOVA model will be used to analyze the additional secondary endpoint. The model will include treatment as a fixed effect, adjusted for baseline KDQOL score, disease type (C3G vs IC-MPGN), and stratification factors. Further details on the presentation of the results are described in Section 6.1. Strategies for addressing ICEs are the same as the ones described in Section 6.4.1. The randomization seed to be used is CCI.

The observed values for KDQOL score will be summarized by treatment group and visit. Summaries will present the descriptive statistics for baseline, absolute values, change and percentage change from baseline data by visit.

All KDQOL score data will be listed for the ITT set.

6.7. Analyses of Exploratory Efficacy Endpoints

All primary, key secondary, and additional secondary endpoints will be evaluated at week 52 as exploratory efficacy endpoints. In addition, the following exploratory endpoints will also be evaluated. Note that this SAP focuses on the analysis of the randomized controlled period (RCP) data only. The analysis for interim data post-week 26 at the time of the datacut will be detailed in an SAP addendum.

6.7.1. The Change From Baseline in uPCR Using the 24-Hour Urine Collections

The observed values for uPCR measured by 24-hour urine collections will be summarized by treatment group and visit using ITT Set. Summaries will present the descriptive statistics for baseline, absolute values, change and percentage change from baseline data by visit.

An MMRM model will be used to analyze the exploratory efficacy endpoint up to week 24. The model will include fixed categorical effects for treatment group, visit, disease type (C3G vs IC-MPGN), stratification factors, and the visit-by-treatment group interactions, as well as the continuous, fixed covariate of baseline 24-hour uPCR values. Further details on the presentation of the results are described in Section 6.1. No multiple imputations will be applied. ICE strategies will be simplified where missing data after the ICEs will be imputed implicitly within the MMRM in a hypothetical strategy under the assumption of MAR.

All 24-hour uPCR data will be listed for the ITT set.

6.7.2. The Annual Rate of Change From up to 3 Years Prior to Screening in eGFR

A generalized linear mixed model will be used to analyze the exploratory efficacy endpoint from up to 3 years prior to screening to the end of the RCP period. The model will include fixed effect for disease type, stratification factors, a common intercept, a pre-treatment (either pegcetacoplan or placebo) slope, and a change in the slope by arm after treatment. Random effects include the individual intercept and slope, and the random errors are i.i.d. normally distributed. The eGFR slope prior to treatment, the slope after pegcetacoplan treatment and the difference comparing to pre-treatment slope, the slope after placebo treatment and the difference comparing to pre-treatment slope, as well as the difference between post-pegcetacoplan slope vs. post-placebo slope, will be summarized along with their 95% CIs and p-values using the ITT set.

In situations where for a certain historical collection, the eGFR value was not collected but the components for calculating it (such as serum creatinine, age, height, etc.) were collected, then the eGFR value will be calculated based on the formula (CKD-EPI creatinine equation for adults or the Bedside Schwartz equation for adolescents) specified in protocol.

6.7.3. The Proportion of Participants With Reductions From Baseline in Proteinuria of at least 30%

The proportion of participants with reductions from baseline in proteinuria (measured by triplicate FMU uPCR) of at least 30% at week 26 will be summarized using ITT set. The baseline and week 26 uPCR calculation will be handled the same way as in Section 6.5.1.

A logistic model will be used to analyze the exploratory efficacy endpoint. The model will include treatment group as the independent variable and adjusted for baseline log-transformed uPCR values, disease type (C3G vs IC-MPGN), and stratification factors. Further details on the presentation of the results are described in Section 6.1. ICE strategies will be the same as those specified in Section 6.5.1.1.

A data listing for each participant's reduction status at week 26 will be provided using ITT set.

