Order of key secondary endpoints revised; change in eGFR at 26 weeks now the last key secondary endpoint	Synopsis Section 5.2.1 Section 12.3.2.1	Based on emerging data and recent expert discussions, histopathologic changes are expected to occur before improvements in eGFR are observed. The order of the key secondary endpoints was amended to prioritize the histopathologic endpoints over the eGFR endpoint.
Removed exploratory endpoint evaluating normalization of hematuria	Section 5.2.1	No post-baseline hematuria evaluations will be conducted.
Removed exploratory endpoint of evaluation of changes in drusen at 26 weeks	Section 5.2.1	If conducted, ophthalmologic evaluations are at baseline and between weeks 42 and 52 only.
Study assessment changes		
Revised description of the window for conducting the optional activities (ophthalmologic evaluations and measured GFR)	Schedule of Activities (Table 2), footnotes t and u Section 10.6 Section 10.7	Description revised to align with study visit schedule.
Safety reporting changes		
Moved definition of TEAEs and the period for recording and reporting TEAEs	Section 11.2.1.1 Section 11.2.2 Section 12.4	Moved so provided with other definitions related to safety reporting.
Statistical analysis changes		
Updated strategies for addressing ICEs	Section 12.3 and subsections	Updated to align with FDA comments.
Revised description of the data review for the analysis set	Section 12.2.7	Revised for clarity.

Description of change	Section(s) affected	Rationale for change
Clarified the analysis set for the evaluation of endpoints related to renal biopsy observations	Section 12.3.2	Revised for clarity.
Study conduct changes		
Added description of the activities at the closure of enrollment	Section 6.2	As the study was approaching target enrollment, the sponsor announced the planned closure of enrollment. Sites continued patient screening activities and all eligible participants were enrolled, resulting in a final enrollment of 124 participants. Added a description to clarify activities at the closure of enrollment.
Revised description of antidrug antibody assessments	Section 11.1.13	Revised to align with current Apellis practice.
Document organization changes		
Added an Appendix containing country-specific modifications to the protocol. Country-specific modifications are noted for Canada, Czech Republic, France, Germany, Netherlands, Israel, Japan, and Switzerland.	Appendix 2	Added to align with current Apellis practice.

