10. ASSESSMENT OF EFFICACY

10.1. Retrospective Data Collection for eGFR and Measured Glomerular Filtration Rate

Retrospective data will be collected on glomerular filtration rate (GFR) to calculate historical eGFR for up to 3 years prior to study entry, depending on the date of diagnosis (for renal transplant recipients, this refers to diagnosis of recurrent disease, not diagnosis of the original disease in native kidneys). Three years of retrospective data will be collected to calculate eGFR for those diagnosed at least 3 years prior to randomization. Retrospective data for the period between randomization and diagnosis will be collected for those diagnosed less than 3 years prior to randomization. For historical eGFR calculations, data will be collected to enable calculation of eGFR by CKD-EPI (with serum creatinine) in adults and by the Bedside Schwartz equation in adolescents. Specifically, age, sex, race, height (adolescents only), serum creatinine, serum blood urea nitrogen (adolescents only), and serum cystatin C (if available) will be collected. For each participant, eGFR will be calculated using the same formula for the duration of the study; the choice of formula will be determined by the participant's age at study entry.

If a participant has historical data on measured GFR, then this data, including the method used to measure GFR, should also be collected (in addition to the data required to calculate eGFR in that participant) for the same timeframe.

10.2. 24-Hour Urine Collection

A 24-hour urine collection is defined as collection of all urine produced over a 24-hour period. As 24-hour urine collections will be done at home, participants will be provided with containers for the collection as well as an instruction sheet that details the collection procedure. The 24-hour urine collection should begin following the first urinary output for the day, and then continue for a 24-hour period. Samples should be collected within ± 1 week of the clinic visit (except for the week 24 collection, which cannot be earlier than week 24).

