3.2. Randomization

Participants will be randomized to receive pegcetacoplan or placebo in a ratio of 1:1 via stratified permuted block randomization. The randomization will be performed centrally. To achieve balance between the arms, 2 stratification factors will be applied to the randomization. The first stratification factor examines participants with posttransplant recurrence versus nontransplant participants; at least 78 participants with C3G or IC-MPGN in a native kidney will be enrolled. This is followed by the second stratification factor, which examines participants with baseline renal biopsies (either collected during screening or a historic biopsy collected within 28 weeks prior to randomization) versus participants without baseline renal biopsies.

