ICE strategies will be the same as the main SAP where the endpoint status at or after the initiation of ICEs will be regarded as non-responder.

6.7.9. The Proportion of Participants with Serum C3 Levels above the LLN at Week 52

The descriptive analysis described in Section 6.6.3 in the main SAP will be repeated at Week 52 based on the ITT Set by using available data through the Week 52 assessment.

ICE strategies will be the same as the main SAP where the endpoint status at or after the initiation of ICEs will be regarded as non-responder.

6.7.10. Change from Baseline in FACIT-Fatigue Scale Score at Week 52

The descriptive analysis described in Section 6.6.4 in the main SAP will be repeated at Week 52 based on the ITT Set by using available data through the Week 52 assessment.

6.7.11. Change from Baseline in KDQOL Score at Week 52

The descriptive analysis described in Section 6.6.5 in the main SAP will be repeated at Week 52 based on the ITT Set by using available data through the Week 52 assessment.

6.7.12. The Change from Baseline in uPCR Using the 24-hour Urine Collections at Week 48

The descriptive analysis described in Section 6.7.1 in the main SAP will be repeated at Week 48 using all available data through the Week 48 assessment based on the ITT Set.

Note for the MMRM modeling for the RCP period, the analysis based on log-transformed 24-hour uPCR will be implemented, instead of the uPCR values on original scale.

6.7.13. The Annual Rate of Change from up to 3 Years Prior to Screening in eGFR

The analysis described in Section 6.7.2 in the main SAP will be repeated at Week 52 using all available data through the Week 52 assessment, with the adjustment that for the placebo group, eGFR data collected during the RCP period will be considered as part of the historical (a.k.a. pre-treatment) data in the analysis. This analysis will be based on the ITT Set.

In addition, the above analysis will be repeated by pooling the two treatment regimens and difference between post-peg and pre-peg will be presented with the 95% CI and p-value.

6.7.14. The Proportion of Participants with Reductions from Baseline in Proteinuria of at least 30% at Week 52

The descriptive analysis described in Section 6.7.3 in the main SAP will be repeated at Week 52 based on the ITT Set by using available data through the Week 52 assessment.

6.7.15. The Proportion of participants with Normalization of Proteinuria at Week 52

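### The exploratory historical eGFR slope model (SAP 6.7.2) has no participant-level random slope change and no stated sandwich SE, so its slope-change intervals are too narrow if that change varies between participants.

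*SAP*

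**What the plan says.** SAP 6.7.2 fits a mixed model to eGFR "from up to 3 years prior to screening to the end of the RCP period". Besides disease type, the stratification factors and a common intercept, its fixed effects are "a pre-treatment (either pegcetacoplan or placebo) slope, and a change in the slope by arm after treatment". The covariance is described in one sentence: "Random effects include the individual intercept and slope, and the random errors are i.i.d. normally distributed". The outputs are the pre-treatment slope and, for each arm, the post-treatment slope and how far it departs from the earlier one. The between-arm contrast is reported too: "as well as the difference between post-pegcetacoplan slope vs. post-placebo slope, will be summarized along with their 95% CIs and p-values using the ITT set".

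The length of history differs between participants. Protocol 10.1 asks for three years of data where diagnosis is that old, and otherwise: "Retrospective data for the period between randomization and diagnosis will be collected for those diagnosed less than 3 years prior to randomization". The schedule of activities gives seven post-baseline eGFR values up to week 26 (weeks 4, 8, 12, 16, 20, 24 and 26).

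SAP 6.1 states a sandwich estimator for two models: the MMRM, and a slope model fitted to baseline and post-baseline data with an unstructured covariance. Section 6.7.2 uses a different model and does not refer to 6.1. The sample code in SAP 17.2.3 is for the uPCR slope.

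Addendum 6.7.13 repeats the 6.7.2 analysis to week 52, with the placebo arm's randomized-period data moved into the pre-treatment segment. It then pools the two regimens: "difference between post-peg and pre-peg will be presented with the 95% CI and p-value".

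**The concern.** The quantity tested is a change in slope, yet the model gives that change no participant-level variance. Everyone in an arm is taken to change slope by the same amount. Any real variation has to be absorbed by the random intercept, the single random slope and the independent residuals, none of which is shaped to carry it. What they fail to absorb is missing from the SE.

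Some variation is plausible. The population mixes C3G with IC-MPGN, native with transplanted kidneys, and adults with adolescents. Protocol 4.2.2 also expects adherence to background medication to shift in either direction after entry, with or without active drug.

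At stake are the only planned contrasts that use pre-treatment eGFR history. The pooled contrast in Addendum 6.7.13 has no concurrent control, so a valid SE is the least it needs.

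**Working it through.** The documents state no figure for this model, so there is nothing to reproduce. The check is how far the model-based SE falls below the true SE.

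**Inputs from the documents.** Total enrolment (Protocol amendment summary): "resulting in a final enrollment of 124 participants". Allocation (SAP 3.2): "Participants will be randomized to receive pegcetacoplan or placebo in a ratio of 1:1 via stratified permuted block randomization". I take this as 62 per arm. Tests are two-sided at 5% (SAP 6).

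**Assumed inputs.** Intercept SD 25, pre-treatment slope SD 5/year and residual SD 6 (mL/min/1.73 m²). History is quarterly: per arm, 36 participants with 3 years, 14 with 2 and 12 with 1. Screening, day 1 and seven post-baseline values are added. The slope-change SD, τ, is varied over 0, 5, 10 and 15 mL/min/1.73 m²/year. There is no arm effect and no mean slope change. Disease type and stratification terms are left out for simplicity.

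**Mechanism.** Let d be time since treatment start (zero before). The true covariance per participant is the SAP model's covariance plus τ²dd′. An unbiased estimate of an arm's slope change puts weights summing to 1 on the individual slope changes in that arm, so τ adds at least τ²/62 per arm, or 2τ²/62 to the between-arm contrast. The SAP model reports almost none of this.

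**Simulation** (400 replicates per scenario, REML, Wald tests, between-arm slope difference):

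| τ | Empirical SE | Model SE | Ratio | Type I error, SAP model | Same model, sandwich SE | With random slope change |
|---|---|---|---|---|---|---|
| 0 | 1.89 | 1.83 | 0.97 | 5.5% | 6.2% | 4.8% |
| 5 | 2.01 | 1.85 | 0.92 | 8.5% | 5.2% | 6.0% |
| 10 | 2.47 | 1.88 | 0.76 | 12.2% | 5.2% | 5.5% |
| 15 | 3.12 | 1.94 | 0.62 | 22.0% | 4.8% | 4.5% |

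Monte Carlo error is 1 to 2 percentage points (one SE). For the within-arm pegcetacoplan slope change, type I error under the SAP model is 5.2%, 8.5%, 14.0% and 23.3%.

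**Second calculation.** With the same three SDs, the ratios r of model SE to true SE are 1.00, 0.92, 0.77 and 0.64. Type I error = 2[1 − Φ(1.96r)] gives 5%, 7%, 13% and 21%.

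**Hand check.** True SE ≈ √(1.83² + 2τ²/62):
- τ = 5: √(3.349 + 0.806) = 2.04; r = 1.85/2.04 = 0.91; about 7.5%
- τ = 10: √(3.349 + 3.226) = 2.56; r = 1.88/2.56 = 0.73; about 15%
- τ = 15: √(3.349 + 7.258) = 3.26; r = 1.94/3.26 = 0.60; about 24%

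These SEs agree with those from the model with a random slope change (2.03, 2.55 and 3.23). The error rates lie slightly above the simulated ones at the two larger SDs, within about two Monte Carlo SEs. I therefore give 12–15% and 21–24% there.

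**The case against.** Several points on the other side stand.

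- **Exploratory only.** The endpoint lies outside the fixed sequence in SAP 6.2, and Addendum 6.2 disclaims formal hypothesis testing of open-label data.
- **Not the only kidney-function contrasts.** A reader might infer that long-run kidney function is judged only here. It is not. SAP 6.5.5.1 (MMRM) and 6.5.5.3.2 (slope) compare eGFR between arms to week 26, and Addendum 6.7.6 does so to week 52. What is unique here is the use of pre-treatment history.
- **Repeats are not treated as independent.** A reader might infer that the model counts every on-treatment value as independent evidence. It does not: the random intercept and slope already induce within-participant correlation. Only the correlation that they fail to capture is ignored.
- **The bias is conditional.** With no variation in slope change the model is calibrated. The 15/year scenario is three times the assumed pre-treatment slope SD, and nothing in the documents supports or excludes it.
- **The sandwich SE may have been intended.** SAP 6.1 introduces its models as the general approach, and the sample slope code requests empirical SEs. If they were meant for 6.7.2 as well, the simulation shows that the problem largely disappears. But the 6.1 slope model differs in data and covariance, and neighbouring sections (6.7.1, 6.7.3, 6.7.4) refer to 6.1 while 6.7.2 does not. The text does not settle it.

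**Conclusion.** The point holds as a conditional one of low severity. As written, SAP 6.7.2 gives intervals that are too narrow and p-values that are too small whenever slope change varies between participants and model-based SEs are used. Under the assumed components, nominal 5% error for the week-26 between-arm contrast becomes 7–9%, 12–15% and 21–24% at slope-change SDs of 5, 10 and 15/year. At zero it stays at about 5%. This is an illustrative range and not a bound.

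The documents do not support saying that the SEs are too small as a matter of fact, since they give no variance components. Nor should these sizes be read across to week 52. Addendum 6.7.13 has the same gap in its random effects, but its altered pre-treatment segment and pooled contrast were not modelled. No primary or key secondary conclusion changes.

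**What to change.** In SAP 6.7.2 and Addendum 6.7.13, do one or both of the following:

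1. Specify a participant-clustered sandwich SE with a small-sample correction. SAP 6.1 already uses the uncorrected form for the other slope models.
2. Add a participant-level random slope change, correlated with the intercept and pre-treatment slope, and name the sandwich SE as the fallback if the model does not converge. Short histories in recently diagnosed participants make a fallback sensible.

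Either remedy brought simulated type I error for the contrasts studied to between 4.5% and 6.5%.

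The Addendum says that the randomized-period analysis was reported in a CSR dated 05 December 2024. For week-26 results already reported, rerun the model as a supplementary analysis.

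The cost is a small re-analysis and wider intervals. With the random slope change, the 95% half-width for the between-arm difference goes from 1.96 × 1.88 = 3.7 to 1.96 × 2.55 = 5.0 mL/min/1.73 m²/year at an assumed slope-change SD of 10. At an SD of 15 it goes from 1.96 × 1.94 = 3.8 to 1.96 × 3.23 = 6.3.
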